9.6.2 Participant tracking log

The list of CYD-TDV exposed pregnant women obtained from Paraná's DoH will also serve as the electronic participant tracking log. The following information will be documented in the tracking log: (i) participant unique, anonymized study ID number; (ii) availability of valid contact information (yes/no); (iii) eligibility status (yes/no); (iv) outcome of each contact attempt and contact dates; (v) participation status (yes/no); (vi) reason(s) for non-participation (e.g., unsuccessful contacts, refused, no signed ICF/AF); (vii) follow-up type (prospective/retrospective/both) if applicable; (viii) withdrawal status (yes/no) if applicable; (ix) study withdrawal date (if applicable); (x) reason(s) for withdrawal (if applicable); (xi) loss to follow-up status (yes/no), and (xii) date of loss to follow-up (if applicable). This information will be used to prepare the study cohort flow diagram.

To comply with data privacy requirements, data collected on the tracking log will be fully anonymized. As such, the final tracking log will not include any nominal data and study participants will be identified using only their unique, anonymized study identification number.

9.6.3 Procedure for withdrawal of study participants

Women and their offsprings followed prospectively may be lost to follow-up or withdraw from the study, which could introduce bias if the loss is related to the outcome of the pregnancy, birth or offspring. Study investigators or their delegate will make every effort to contact prospectively followed study participants at the pre-specified time points to determine their health status and that of the offsprings. In addition, the relatively short period of follow-up in this study (approximately 18 to 20 months depending on the timing of the reporting of pregnancy exposure) will help to minimize the risk of losses to follow-up, as will obtaining contact information for a close friend/contact not living in the same household as the study participant (i.e., additional source of information for tracking study participants). The impact of losses to follow-up and study withdrawal will also be mitigated by the use of medical records review and linkages with available health and mortality databases to obtain

outcomes data. In this way, outcome ascertainment will be possible even for those lost to follow-up.

9.7 DATA ANALYSIS

The statistical analysis will be conducted under the responsibility of Sanofi Pasteur's Biostatistics platform using SAS® software, version 9.4 or above (SAS Institute, Cary, NC, USA).

9.7.2 Secondary analysis

Descriptive analyses will also be undertaken to characterize pregnancy exposure with regards to number of doses received (during the pregnancy and overall), dose intervals, and trimester of exposure (including a stratum for the preconception period), as well as to characterize the population of pregnant women inadvertently exposed to CYD-TDV (see Appendix 5).

9.7.3 Interim analysis

No interim analysis is planned for this registry study as the number of events is expected to be very small given the rarity of these and the small sample size. Nevertheless, some descriptive analyses will be conducted at regular intervals corresponding to the Periodic Benefit-Risk Evaluation Report (PBRER), and included in updates of the risk management plan (RMP) associated with regulatory submissions. The latter analyses will be described in a specific Statistical Analysis Plan (SAP).

9.7.4 Sensitivity analyses

The following sensitivity analyses will be undertaken to test the robustness of the results:

- The primary analysis will be repeated restricted to women receiving care from the public health care sector only as SIPNI/EAPV includes women from both the private and public sector but outcome data for women receiving care in the private sector will be limited to those that are self-reported as the available health and mortality databases reflect care provided in the public sector and the medical records of women in the private sector may not be accessible. Women receiving care from both sectors will be classified as having a private coverage.
- To address the possibility of bias owing to the retrospective nature of some outcomes data, the analysis will be repeated stratified by the nature of the outcomes (i.e., prospective vs. retrospective).
- To address the possibility of misclassification of exposure due to the use of a “30 days prior to the LMP” conservative criteria for the definition of “exposed pregnancy,” the analysis will be repeated excluding pregnancies and offsprings exposed during the preconception period (LMP - 30days) if available data permits.
- To address potential bias introduced by study participants who did not consent to medical chart review and/or database linkages, the analyses will be repeated by excluding these study participants.

9.8 QUALITY CONTROL

This study will be conducted in accordance with the Guidelines for Good Pharmacoepidemiology Practices (GPP) of the International Society for Pharmacoepidemiology (ISPE) [Revision 3, 2015], and the European Network of Centres for Pharmacoepidemiology and Pharmacovigilance (ENCePP) Guide of Methodological Standards, Revision 4, 2015. This will be ensured at an operational technical level by requiring the use of formal procedures for testing and validating all software and databases developed for the project, and by developing early in the project, quality guidelines that affect all work and procedures to be implemented.

Data quality will also be assured through routine monitoring by the Sponsor or delegate, and through periodic cross-checks against the protocol.

9.8.1 Assessment of validity and representativeness of study results

Each data source to be used in this pregnancy registry study has strengths and limitations; therefore, their combined use will leverage their respective strengths and significantly improve overall data quality. For example, the literature suggests that the first antenatal visit is well documented in SISPRENATAL, while subsequent visits

are less complete than that recorded in the prenatal care booklet;¹¹ therefore, use of both data sources will improve the overall study data quality. Similarly, women's self-reported outcomes will be compared to those recorded in their medical records and the health and mortality databases administered by Brazil's MoH and Paraná's DoH.

For women enrolled retrospectively (i.e., outcomes occurred before study enrollment), study outcomes will be known at the time of data collection, thereby increasing the risk of reporting or recall bias, as well as the risk of ascertainment or detection bias. For example, since CYD-TDV is known to be contraindicated in pregnancy, it is possible that concerned exposed pregnant women would pay closer attention to their health and that of their offsprings. Similarly, physicians and health care providers (HCPs) may undertake more intensive follow-up of exposed pregnant women and their offsprings than of their unexposed counterparts in the general population. Both of these scenarios could result in the detection of more AEs for study participants and their offsprings. It is also conceivable that study participation could be affected by knowledge of outcome status at the time of data collection. For example, exposed pregnant women who experienced a serious complication of pregnancy could be more likely to participate if they wanted to ensure the event was captured and/or reported or, they could be less willing to participate if they were upset or traumatized by the event. Consequently, the direction of the bias resulting from differential participation will be hard to predict in the absence of data on non-participants to assess the presence and direction this source of bias. Moreover, incomplete participation could also affect the generalizability of study results.

As the scenarios described above represent important threats to the validity of the results and to their generalizability, permission will be sought from the Ethics Committee to obtain *aggregate level* information (i.e., anonymized data) on rates of pregnancy, birth, neonatal and infant outcomes of special interest for non-participants, as well as *aggregate level* information on the baseline characteristics and characteristics of prenatal care of non-participants obtained from the MoH and DoH databases to enable a comparison of participants and non-participants, and assess the likelihood, strength and direction of the aforementioned biases. This comparison will also provide an assessment of the representativeness of the pregnancy registry participants.

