databases (secondary data sources). Study participation will require receipt of a signed informed consent form (ICF) or Assent form (AF) according to local regulations. CYD-TDV exposed pregnant women will be actively identified and recruited using pregnancy exposures reported to the national spontaneous adverse events following immunization reporting system (SI-PNI EAPV). As such, women included in the pregnancy registry will represent those receiving care in the public and private health care settings at the time of their pregnancy exposure. The start of follow-up for the pregnant women will be the date of first CYD-TDV vaccination during the exposed pregnancy and the date of birth for the offsprings. Study outcomes will include maternal, pregnancy, birth, neonatal and infant AESIs, as well as all other reported AEs. Study data will be collected by the study investigators (or research personnel designated by the investigators) through home visit and/or telephone interviews using a structured questionnaire. Self-reported information will be supplemented and confirmed through contact with the woman's physician or other health care provider (e.g., nurse), use of medical records (e.g., prenatal care booklet, hospital, primary health care unit or other settings where antenatal care was provided), and use of record linkages with existing databases (e.g., SINASC, SIM), subject to availability. In cases of discrepancies between data sources, the medical record will be used as the gold standard for most data, followed by databases. Women will be followed for 42 days after the end of pregnancy, irrespective of the duration of the pregnancy, and their offsprings will be followed for up to 12 months post-birth.

* Exact date will depend on timing of local and national EC approvals

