Gravidity	Collected from the questionnaire; total number of confirmed pregnancies regardless of the outcome
None	
1	
≥2	
Parity	Derived from Gravidity & question on number of pregnancies births Collected from the questionnaire; total number of births with >20 weeks gestation
None	
1	
≥2	
Previous miscarriage/spontaneous abortion (yes/no)	Collected from the questionnaire
Previous preterm birth (yes/no)	Collected from the questionnaire
Previous dengue infection	Collected from the questionnaire
Unknown	
Confirmed (describe method)	
Clinically diagnosed/unconfirmed	
Preexisting comorbidities (yes/no)	Collected from the questionnaire; confirmed using medical record review and/or health databases when available
Hypertension	
Diabetes	
Type I diabetes	
Type II diabetes	
Pulmonary disease (specific type)	
Heart disease (specify type)	
Renal disease (specify type)	
Vaccination and medication history	
Receipt of other vaccine(s) during pregnancy (specify)	Collected from the questionnaire, as well as from the “vaccination card” and/or “prenatal booklet” when available
Receipt of medications during pregnancy (specify)	Collected from the questionnaire; included prescription and non-prescription medications
Characteristics of prenatal care and delivery	
Gestational age at first prenatal visit, weeks	Derived from gestational age at first CYD-TDV vaccination

	during pregnancy & date of first prenatal visit; the latter should be available from either SISPRENATAL or the prenatal booklet
Number of prenatal care visits, mean (SD)	Collected from either SISPRENATAL or the prenatal booklet when available
Referral to specialist care (specify type of specialist)	Collected from the questionnaire and confirmed using SISPRENATAL or the prenatal booklet when available
Number of ultrasounds, mean (SD)	Collected (if data is available)
Index of prenatal care	Derived from number of prenatal care visits recorded in the prenatal booklet and/or SISPRENATAL when available
Adequate/plus (≥ 7 visits)	
Intermediate (3-6 visits)	
Inadequate (<3 visits)	
Hospitalization(s) during pregnancy	Collected from the questionnaire; confirmed using SISPRENATAL or the prenatal booklet or review of hospitalization records when available
Hospitalization <20 weeks gestation	
None	
1	
≥ 2	
Hospitalization ≥ 20 weeks gestation	
None	
1	
≥ 2	

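### Section 9.8.1 fixes a database-only source for non-participants but not for participants, so their comparison can show a difference without participation bias, or hide a real one

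*Protocol*

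**What the plan says.** Protocol section 9.8.1 plans, subject to Ethics Committee permission, to compare participants with non-participants. The aim is to judge whether the biases it describes are present, how strong they are and which way they run, and whether the registry is representative. The aggregate data sought include "characteristics of prenatal care of non-participants obtained from the MoH and DoH databases to enable a comparison of participants and non-participants". They also include "rates of pregnancy, birth, neonatal and infant outcomes of special interest for non-participants". For these outcomes no source other than the databases is described, and non-participants have not agreed to an interview or a chart review.

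Participants are measured from more sources:

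- Appendix 5, number of prenatal visits: "Collected from either SISPRENATAL or the prenatal booklet when available".
- Appendix 5, prenatal care index, whose top category starts at seven visits: "Derived from number of prenatal care visits recorded in the prenatal booklet and/or SISPRENATAL when available".
- Section 9.1.1, where sources disagree: "the medical record will be used as the gold standard for most data, followed by databases".
- Appendix 4 defines seven neonatal events (pneumonia, respiratory distress syndrome, transient tachypnea, pulmonary hypertension, encephalopathy, seizures, sepsis) by the clinician's assessment in the medical record alone.

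The protocol also states that these sources differ. Section 9.8.1 says that visits after the first, as held in SISPRENATAL, "are less complete than that recorded in the prenatal care booklet". Section 9.4 describes SISPRENATAL as a public-sector database. Section 9.7.4 says that "outcome data for women receiving care in the private sector will be limited to those that are self-reported", because the databases reflect public care and private records may not be accessible.

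**The concern.** A check for participation bias needs the two groups to be measured in the same way. Here the protocol fixes the source for one group and leaves the other to general definitions that use richer sources. If those definitions are followed, a gap can arise because the booklet records more visits than SISPRENATAL, or because a participant's interview or chart reveals events that no database holds.

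The error can also run the other way. Section 9.8.1 itself considers that women with a serious complication might decline to take part. If events in non-participants are under-recorded, a true excess among them can disappear and the registry can look representative when it is not.

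The same section says that the direction of participation bias is hard to predict without data on non-participants, so the reading of the main results leans on this comparison. Section 9.9 offers it as the answer to that limitation and does not list the difference in sources among the study's limitations.

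**Working it through.** **The plan's own figures.** The protocol gives no figure for this comparison. Its only statistical table, the confidence intervals in section 9.5, reproduces as exact Clopper-Pearson intervals (for example 31/214 gives 10.06 to 19.93). One upper limit comes out at 3.43 against 3.42, which is rounding. That table is not in dispute. It supplies the group sizes below: 214 reported exposures, with 107 participants at 50% participation, or 160 at 75% (leaving 54 non-participants).

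**Assumptions, none given in the protocol.** Care is identical in both groups. Total visits are 1 + Poisson(7), a mean of 8. The first visit is always recorded. The booklet is complete and available for every participant. SISPRENATAL captures each later visit with probability c.

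**Visit index.** Recorded later visits are Poisson(7c), and seven or more visits in total needs six or more later ones. So the share in the top category is P(Poisson(7c) ≥ 6).

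| c | 7c | Share with ≥7 visits | Gap from booklet | Chance of p<0.05, 107 v 107 | Chance of p<0.05, 160 v 54 |
|---|---|---|---|---|---|
| 1 (booklet) | 7.0 | 69.9% | – | – | – |
| 0.9 | 6.3 | 60.1% | 9.8 points | 32% | 27% |
| 0.8 | 5.6 | 48.8% | 21.1 points | 89% | 80% |
| 0.7 | 4.9 | 36.6% | 33.3 points | >99% | 99% |

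The last two columns take a two-sided 5% comparison of proportions. The protocol names no test, so they only indicate how visible the gap would be.

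**Sensitivity to the mean.** With a mean of 7 visits the shares are 55.4% by booklet against 45.4%, 34.9% and 24.7% (gaps of 10.0, 20.5 and 30.7 points). With a mean of 9 they are 80.9% against 72.4%, 61.6% and 48.8% (gaps of 8.5, 19.3 and 32.1 points).

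**Sensitivity to booklet availability.** If half of the participants were scored from SISPRENATAL, each gap would halve. At a mean of 8 it would be about 5, 11 and 17 points.

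**Outcomes.** Let the true risk be 14.3% in both groups (the section 9.5 figure for spontaneous abortion, used here only as a scale), with full capture in participants and database sensitivity s in non-participants. The observed non-participant risk is 14.3% × s: 11.4% at s = 0.8, 7.1% at s = 0.5 and 1.4% at s = 0.1. With 107 v 107 the chance of p<0.05 is 9%, 39% and 94%. The protocol gives no value of s, so the effect runs from negligible (s near 1) to large (s near 0).

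**Masking.** If the true risk in non-participants were 1.4 times that in participants and databases captured 71% of their events, the observed ratio would be 1.4 × 0.71 = 0.99.

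**Same source in both groups.** With database values and the same definitions on both sides, capture applies equally. The expected difference without participation bias is then zero, provided capture does not itself differ between the groups. That is why the public/private mix has to be handled.

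**The case against.** The strongest reply is that section 9.8.1 never says which participant values enter the comparison. The definitions in section 9.1.1 and Appendix 5 serve the main dataset and baseline table, and section 9.8.2 keeps the SISPRENATAL, SINASC and SIM extracts as separate databases. A like-for-like table is therefore possible, and choosing it could be left to the SAP. This stands as far as it goes: the mismatch follows from applying the protocol's definitions and is not a stated instruction. But the protocol fixes one group's source and the inference to be drawn. The non-participant data will also arrive as aggregates, which cannot readily be re-cut, so the items and definitions should be settled before they are requested.

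Other points also stand:

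- Appendix 5 allows SISPRENATAL as well as the booklet, and booklets from past pregnancies may be missing, so the illustrated gaps are upper values for each capture rate.
- Section 9.4 describes SINASC and SIM as national databases. For birth condition, recorded malformations and deaths, both groups have much the same source.
- Section 9.8.1 names recall and detection bias as well as differential participation, so a reader should not infer that every gap is to be read as participation bias.
- The comparison is a quality check that depends on permission. It changes no reported risk, and the tracking log in section 9.6.2 also records reasons for non-participation.

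A reader might infer that the comparison is bound to show a difference. The documents do not support that: the participant source is open, capture is not quantified, and at 90% capture the spurious gap would reach p<0.05 only about 30% of the time.

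**Conclusion.** The concern holds in a limited form. The protocol sets a database-only source for non-participants, does not require the same source for participants, and itself says that the sources differ in completeness and coverage. The comparison can therefore show a gap without participation bias, or conceal a real one. The exposed items are visit count, the prenatal care index, the chart-defined neonatal events and any result for private-sector women.

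For the visit index the spurious gap is about 10 to 33 percentage points at 90% to 70% capture. This assumes a mean of 8 visits and a complete booklet for all participants, and the gap is smaller as more participants are scored from SISPRENATAL. For outcomes no size can be given, because database sensitivity is not stated. The smaller effect for birth condition and deaths rests on section 9.4's account of SINASC and SIM as national. Section 9.7.4 speaks more broadly of the health and mortality databases as reflecting public care.

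This is a cheap improvement to a supporting check, not an error in the main results.

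**What to change.** State in section 9.8.1 that the comparison of participants with non-participants uses, in both groups, only values from the MoH and DoH databases, with the same definitions, and is limited to items that those databases hold. Restrict SISPRENATAL-based items to public-sector care, with the sector assigned by one rule that the databases allow for both groups.

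Section 9.2.5.1 admits women who refuse database linkage. Report how many participants lack linkage consent and are therefore left out of this comparison. Keep the multi-source participant values for the main results. Showing participants' multi-source and database-only values side by side would also give a direct measure of how much the databases miss.

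The cost is a few sentences and one extra tabulation from extracts that are already planned. The downside is that unlinked participants, and items that the databases do not hold, such as chart-only neonatal events, drop out of this check.

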9.8.2 Data collection, validation and quality control

The Principal Investigator (PI) will be responsible for overall quality assurance at the study site(s).

Study data obtained from the structured interviews and medical record reviews (primary data) will be entered into an electronic case report form (eCRF). Quality control in the form of computerized logic (e.g., to detect "out of range" entries) and/or consistency checks will be systematically applied to detect errors and omissions. In addition, data reviews will be performed by the Sponsor or their delegate (e.g., CRO) over the course of the study. Any questions pertaining to the collected study data will be submitted to the investigator(s) for resolution using the EDC system. Each step of this process will be monitored through implementation of individual passwords to ensure appropriate database access and database integrity.

Review of the data will be through the data review process led by Data Management.

Following the: (i) integration of all corrections in the dataset of primary data, (ii) the reconciliation of AE information available from the CDM and the GPV databases,

and (iii) assessment of the MoH and DoH databases (secondary data) for missing and out-of-range data, the research databases will be released for statistical analysis.

Data extracted from the MoH and DoH existing health and mortality databases (e.g., SISPRENATAL, SINASC, SIM) already exist in an electronic format and will, therefore, not require data entry, nor be included in the EDC system. As such, they will be maintained in their original electronic format as separate databases. However, in order to anonymize these databases prior to analysis, individuals' nominal data will be replaced by their unique study identification number by the study investigators or their delegate(s).

The data collection and validation procedures will be detailed in appropriate operational documents.

